Fasting Visit ^d			X				X				X		X		X	X	X		X	X	X
Telephone Visit				X		X		X		X		X		X							
Laboratory Tests																					
Serum pregnancy test ⁿ	X																				
Urine pregnancy test ^o			X										X				X		X		
Follicle-stimulating hormone test ^p	X																				
Chemistry panel	X ^q												X				X		X	X	X
Fasting serum glucose			X				X				X		X		X	X	X		X	X	X
Lipid panel			X																X	X	X
Urinary albumin/creatinine ratio	X ^q																		X	X	X
Serum creatinine, eGFR (CKD-EPI) ^r	X ^q												X				X		X	X	
Calcitonin	X ^q												X				X		X	X	X
Hematology	X ^q												X				X		X	X	X
HbA1c	X		X				X				X		X		X	X	X		X	X	X
Pancreatic amylase, lipase	X ^q												X				X		X	X	X
Immunogenicity ^s			X				X						X				X		X	X	X
PK sample for Immunogenicity ^t			X				X						X				X		X	X	X

	Study Period I		Study Period II																	Study Period III	
	Screening Lead in		Treatment Period																	Safety F/U	
Visit	1	2	3 ^a	4	5	6	7	8	9	10	11	12	13	14	15	16	17	18	19	ET ^b	801
Week of Treatment	-3	-2	0	1	2	3	4	5	6	7	8	10	12	14	16	20	24	32	40		4 weeks Post End of Tx
Allowable Deviation (days) ^c	-	±3	±7	±3	±3	±3	±3	±3	±3	±3	±3	±3	±3	±3	±3	±3	±3	±7	±7		±7
Fasting Visit ^d			X				X				X		X		X	X	X		X	X	X
Telephone Visit				X		X		X		X		X		X							
Anti-GAD antibody			X																		
Patient Reported Outcomes ^e																					
APPADL			X																X	X	
EQ-5D-5L			X																X	X	
IW-SP			X																X	X	
DTSQs			X																		
DTSQc																			X	X	

Abbreviations: APPADL = Ability to Perform Physical Activities of Daily Living; BG = blood glucose; BP = blood pressure; CKD-EPI = Chronic Kidney Disease-Epidemiology; DTSQc = Diabetes Treatment Satisfaction Questionnaire change; DTSQs = Diabetes Treatment Satisfaction Questionnaire status; eGFR = estimated glomerular filtration rate; EQ-5D-5L = European Quality of Life- dimensions; ET = early termination; F/U = follow-up; GAD = glutamic acid decarboxylase; HbA1c = hemoglobin A1c; PR = pulse rate; IW-SP = Impact of Weight on Self Perception; PK = pharmacokinetics; SMBG = self-monitored blood glucose; TTT = treat to target; Tx = treatment.

- ^a Baseline assessments must be completed before processing in the interactive web-response system.

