- ^b Patients who are unable or unwilling to continue in the study for any reason will perform an ET visit. If the patient is discontinuing during an unscheduled visit, that visit should be performed as the ET visit. If the patient is discontinuing during a scheduled visit, that visit should be performed as an ET visit. Visit 801 (safety follow-up visit) should be performed 4 weeks after the ET visit as the final study visit.
- ^c The visit date is determined in relation to the date of the randomization visit (± the allowed visit window).
- ^d On visits 3, 7, 11, 13, 15, 16, 17, 19, ET, and at follow-up, patients should be reminded to report to the site in a fasting condition, after a period of approximately 8 hours without eating, drinking (except water), or any significant physical activity and before taking study drug(s), metformin and sulfonylurea (if used).
- ^e Medical history includes assessment of preexisting conditions (including history of gallbladder disease, cardiovascular disease, and medullary thyroid carcinoma) and substance usage (such as, alcohol and tobacco).

- ^f Weight measurements must be in kilograms.
- ^g Vital sign measurements should be taken before obtaining an ECG tracing and before collection of blood samples for laboratory testing, at visits where required. The participant should sit quietly for 5 minutes before vital sign measurements are taken. For each parameter, 2 measurements will be taken using the same arm; the recordings should be taken at least 1 minute apart. BP must be taken with an automated blood pressure machine.
- ^h Dilated fundoscopic examination will be performed for all patients between Visit 2 and Visit 3, unless there is a contraindication to dilate the eye (ie. closed angle glaucoma). The diagnosis will be made by an eye care professional (ophthalmologist or optometrist) before Visit 3 to exclude patients with proliferative diabetic retinopathy and/or diabetic maculopathy or nonproliferative diabetic retinopathy that requires acute treatment. The results from this examination will be recorded on a specific retinopathy eCRF as a baseline measure of retinopathy. Follow up dilated fundoscopic examination should be performed when clinically indicated, and the results recorded on the retinopathy eCRF.
- ⁱ Includes counseling on diet and exercise, symptoms and management of hypoglycemia, etc.
- ^j All training should be repeated as needed to ensure patient compliance.

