10.3.3. Efficacy Analyses

10.3.3.1. Primary Analyses

The primary objective of this study is to establish noninferiority of 10 mg tirzepatide and/or 15 mg tirzepatide to insulin glargine relative to mean change in HbA1c from baseline to the 40-week visit.

The primary efficacy analysis will be based on the contrast from the MMRM analysis using EAS. The response variable of MMRM will be change in HbA1c from baseline values obtained at each scheduled postbaseline visit. The independent variables of the MMRM model are treatment group (5 mg tirzepatide, 10 mg tirzepatide, 15 mg tirzepatide, and insulin glargine), visit, and treatment-by-visit interaction, country, sulfonylurea use (Yes or No), and baseline HbA1c as a covariate. An unstructured covariance structure will model relationship of within-patient errors. If the analysis fails to converge, the following variance-covariance matrices will be used (in order) until convergence is achieved: heterogeneous compound symmetry, compound symmetry, and first-order autoregressive. The Kenward-Roger approximation will be used to estimate denominator degrees of freedom. With the aid of the MMRM analysis, 2-sided 97.5% CIs for the difference in mean change in HbA1c from baseline to the 40-week visit between 10 mg tirzepatide and insulin glargine as well as between 15 mg tirzepatide and insulin glargine will be constructed. If the upper limit of the CI is below 0.4%, the tirzepatide dose will be declared noninferior to insulin glargine.

Additional details, including analysis methods for key secondary endpoints and a strategy for controlling the overall family-wise type 1 error rate at an alpha of 0.05 for primary and key secondary endpoint evaluation will be provided in the SAP.

Additional Analysis for the Primary Endpoint

The primary analysis model, MMRM, will be repeated using the PP populations to check the sensitivity of the analysis. If the conclusion differs from that of all randomized patients, the data and analyses will be further investigated. Details for the analysis conducted on PP population will be included in SAP.

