6.12.1.1. Primary Analysis Model

The analysis will be conducted utilizing HbA1c data in EAS from baseline through the 40-week visit with the aid of a mixed model for repeated measures (MMRM). Restricted maximum likelihood (REML) will be used to obtain model parameter estimates and Kenward-Roger option will be used to estimate denominator degrees of freedom. The response variable of the MMRM model will be the primary measure and model terms will include treatment, visit, treatment by visit interaction, country, and baseline concomitant oral antihyperglycemic medication use (metformin alone versus metformin plus SU) as fixed effects, and baseline HbA1c as a covariate. An unstructured covariance structure will be used to model the within-patient errors. If this model fails to converge, the following covariance structures will be tested in order:

- heterogeneous Toeplitz;
- heterogeneous First Order Autoregressive;
- heterogeneous Compound Symmetry;
- Toeplitz;
- first Order Autoregressive;
- compound Symmetry.

The first covariance structure that converges will be used. The resulting least squares mean (LSM) estimates of mean change from baseline in HbA1c will be plotted by visit and by study treatment.

With the aid of the MMRM analysis, 2-sided 97.5% confidence interval (CI) for mean change in HbA1c from baseline to 40-week visit for (10 mg tirzepatide - insulin glargine) as well as for (15 mg tirzepatide - insulin glargine) will be derived. If the upper limit of the CI is $\leq 0.4\%$, then the respective dose of tirzepatide (10 mg and/or 15 mg) will be declared noninferior to insulin glargine relative to change in HbA1c from baseline.

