6.13. Safety Analysis

Unless specified otherwise, safety assessments will be based on the SS ([Table GPHO.6.1](#)). All events that occur between the date of first dose of study drug to the date of patient's safety follow-up visit or patient's end of study participation will be included, regardless of the adherence to study drug or initiation of rescue therapy. The events occurring on the day of the first dose of study medication will be counted as post-treatment. For assessing benefit and risk profile through 40-weeks, selected safety analyses will be conducted by utilizing safety data from first dose through the date of 40-week visit. Some safety analyses may be conducted after excluding data after the initiation of new antihyperglycemic therapy. Unless specified otherwise, statistical assessment of homogeneity of the distribution of categorical safety responses among treatment arms will be conducted using Fisher's exact test.

The mean change from baseline difference among treatment at all scheduled visits will be assessed via a MMRM using REML. The model will include country, baseline HbA1c ($\leq 8.5\%$, $> 8.5\%$ [≤ 69 , > 69 mmol/mol]), baseline concomitant oral antihyperglycemic medication, treatment group, visit, and treatment-by-visit interaction as fixed effects, and baseline value of the safety parameter as a covariate. To model the covariance structure within patients, the unstructured covariance matrix will be used. If this model fails to converge, the covariance structures will be tested in order specified in Section 6.12.1.1.

For selected safety parameters, time-to-first-event analysis via the cox-proportional hazards model may be conducted. Patients without the event will be censored at the end of study participation. For patients experiencing the event, the “time-to-first-event” will be the time (in days) from first dose to first occurrence of the event.

Where necessary, the rate of events will be analyzed using a generalized linear mixed-effects model assuming the number of events follow a negative binomial distribution, and with treatment as a fixed effect. The logarithm of days during the active treatment period will be adjusted as an offset to account for possible unequal treatment duration of follow-up between patients.

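### If the unstructured HbA1c model fails to converge, the first two fallback covariances treat the 16-week gap before Week 40 as a 4-week gap; this is unlikely to be needed and cheap to fix

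*SAP*

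**What the plan says.** SAP 6.12.1.1 fits HbA1c change from baseline on the efficacy analysis set by REML with Kenward-Roger degrees of freedom. The planned covariance is clear: "An unstructured covariance structure will be used to model the within-patient errors". The contingency follows: "If this model fails to converge, the following covariance structures will be tested in order". Six structures are listed, in this order: heterogeneous Toeplitz, heterogeneous AR(1), heterogeneous compound symmetry, Toeplitz, AR(1), compound symmetry. The choice is mechanical: "The first covariance structure that converges will be used". No actual-time structure, ante-dependence structure or robust variance is named.

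The protocol (10.3.3.1) gives a different and shorter list: "heterogeneous compound symmetry, compound symmetry, and first-order autoregressive". SAP 6.13 sends the safety models to the SAP list: "the covariance structures will be tested in order specified in Section 6.12.1.1". SAP 6.14 does the same for vital signs.

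In the Schedule of Activities (Protocol Section 2) the HbA1c row is marked after baseline at Visits 7, 11, 13, 15, 16, 17 and 19, that is Weeks 4, 8, 12, 16, 20, 24 and 40. Visit 18 (Week 32) has no HbA1c. These are also the fasting visits of footnote d: "On visits 3, 7, 11, 13, 15, 16, 17, 19, ET, and at follow-up". SAP 6.4 states that the MMRM handles missing data through its variance-covariance structure.

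**The concern.** Toeplitz and AR(1) structures index correlation by the number of visits apart, not by weeks. With gaps of 4, 4, 4, 4, 4 and 16 weeks, they give Weeks 24 and 40 the same correlation as Weeks 20 and 24. If correlation falls with time, that is wrong at the one interval the primary comparison depends on, because a missing Week-40 value is predicted largely from Week 24.

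The efficacy analysis set drops data after rescue. One rescue criterion (Protocol 7.7.2, item d) is triggered by HbA1c at Week 24 itself, and the hyperglycemia criteria apply to the glargine arm only after Week 16. Loss that depends on HbA1c and differs by arm is therefore possible. At stake are the standard error, and under such loss the estimate, for HbA1c noninferiority and superiority.

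**Working it through.** **1. The plan's own power.** Inputs from SAP 5.2: difference 0.45, SD 1.2, two-sided alpha 0.025 per dose (z = 2.241), 25% rescued or discontinued, 239 per arm.
- Evaluable n = 239 × 0.75 = 179.25. SE = 1.2 × √(2/179.25) = 0.1268. Power = Φ(0.45/0.1268 − 2.241) = 90.5% (stated: at least 90%).
- China only (80% of that n): 82.5% (stated: 82%).
- Noninferiority, distance 0.45 + 0.40 = 0.85: Φ(0.85/0.1268 − 2.241) > 99.9% (stated: >99%).

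The plan's figures reproduce. It gives none for the fallback.

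**2. Assumptions, not in the documents.** Correlation at lag d weeks = c + (1 − c) × [(r − c)/(1 − c)]^(d/4), with 4-week correlation r = 0.8 or 0.9 and floor c = 0 or 0.5. This gives Week 24–40 correlations of 0.41, 0.56, 0.66 and 0.70. Week-40 SD is 1.2, with visit SDs constant or rising from 0.6; the SEs are the same either way. 25% of Week-40 values are missing at random in each arm.

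**3. Fit.** Each working structure was fitted to the assumed covariance by expected Gaussian likelihood. The model-based SE of the Week-40 difference was compared with the true (sandwich) SE of the same estimator, at 239 per arm.

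| r, c | True Week 24–40 correlation | Unstructured SE | Het. Toeplitz: model / true (ratio) | Het. AR(1): model / true (ratio) | ANTE(1) SE (ratio) |
|---|---|---|---|---|---|
| 0.8, 0 | 0.41 | 0.1241 | 0.1449 / 0.1269 (1.14) | 0.1445 / 0.1270 (1.14) | 0.1241 (1.00) |
| 0.8, 0.5 | 0.56 | 0.1204 | 0.1303 / 0.1217 (1.07) | 0.1337 / 0.1227 (1.09) | 0.1216 (1.00) |
| 0.9, 0 | 0.66 | 0.1197 | 0.1407 / 0.1212 (1.16) | 0.1398 / 0.1213 (1.15) | 0.1197 (1.00) |
| 0.9, 0.5 | 0.70 | 0.1183 | 0.1329 / 0.1195 (1.11) | 0.1346 / 0.1196 (1.13) | 0.1186 (1.00) |

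The two fallbacks fit a Week 24–40 correlation of 0.75–0.87 and a Week-40 SD of 1.34–1.48 instead of 1.20. Heterogeneous compound symmetry gave ratios of 1.04–1.08.

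Hand check of the first row: unstructured SE = √{(2 × 1.2²/239) × [(1 − R²)/0.75 + R²]} with R² = 0.41² = 0.168, which gives 0.124. Putting in the fitted AR(1) values (SD 1.48, R² = 0.75² = 0.5625) gives 0.145.

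**4. Power.**
- Unstructured: Φ(0.45/SE − 2.241) = 92–94%.
- Heterogeneous Toeplitz, model SE in the same formula: Φ(0.45/0.1449 − 2.241) = 81% up to Φ(0.45/0.1303 − 2.241) = 89%.
- That formula takes the inflated SE as the sampling spread too. The actual rejection rate is Φ((0.45 − 2.241 × model SE)/true SE). In the first row this is Φ((0.45 − 0.3248)/0.1269) = 84%; over all rows it is 84–90%.
- Noninferiority, first row: Φ((0.85 − 0.3248)/0.1269) > 99.9%.

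**5. Bias in the treatment difference.** This was a separate large-sample fit with dropout spread over visits: 25% per arm, driven by high HbA1c in glargine and random in tirzepatide.
- Heterogeneous Toeplitz: −0.06 to −0.09, favouring tirzepatide, with one-sided noninferiority error 0.020–0.025 against a nominal 0.0125.
- Heterogeneous AR(1): −0.01 to −0.10.
- Unstructured: at most 0.002 in size.
- At 10% dropout, the two fallbacks gave −0.01 to −0.04.
- With random loss, the same mechanism in both arms, or complete data: about 0.

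In this set-up the heterogeneous Toeplitz SE was 9–20% too large.

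**The case against.** **The step may never be used.** An unstructured 7 × 7 matrix has 7 × 8/2 = 28 parameters. About 956 patients contribute, with some 956 × 0.75 = 717 evaluable at Week 40. Failure is unlikely. This stands, and it sets the severity.

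**The misfit cannot be verified.** It needs the Week 24–40 correlation to be well below the Week 20–24 value. That is plausible, but the documents give no correlation, so the sizes are conditional. This stands.

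**Stronger readings that a reader might infer:**
- *That the fallback makes false claims easier in general.* The SE error of the first two fallbacks is conservative. Noninferiority error rose only where HbA1c-dependent loss differed by arm.
- *That a shift in one arm's mean is a treatment-effect bias.* If the lost patients are 1.0% higher at Week 24, an arm mean moves by 0.06–0.12, but the planned 0.45 is a between-arm difference, and equal shifts cancel.
- *That every endpoint sharing the list has this gap.* Weight, waist circumference and vital signs are also measured at Week 32, so their last gaps are 8 weeks. Fasting serum glucose follows the HbA1c visits and does share it, but is outside the type I error control.
- *That the differing protocol list is itself an error.* Both documents allow non-principal methods to change in the SAP. At most, a stated reason is missing.

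**There is a partial check elsewhere.** The ANCOVA on the full analysis set (SAP 6.12.1.2) uses only baseline and Week 40 and does not depend on this covariance. It has the same interval and margin, but it is labelled a sensitivity analysis and does not repair the primary one.

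**Conclusion.** The point holds as a conditional, low-severity weakness. If the unstructured HbA1c fit fails, the rule moves first to two structures that cannot represent the visit spacing and reports a model-based SE. When correlation falls with time, within the assumed range and with 25% missing at Week 40, that SE is about 7–16% too large. The cost is superiority power, about 3–11 percentage points depending on scenario and formula; noninferiority at the planned effect is not threatened. A between-arm bias of about 0.06–0.09 for heterogeneous Toeplitz needs HbA1c-dependent rescue or discontinuation that differs by arm, and is near zero otherwise. The documents do not support saying that the primary analysis as planned is wrong: under the unstructured matrix the SE was correct and bias negligible in every set-up tried.

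**What to change.** In SAP 6.12.1.1:
1. If the unstructured fit fails, first retry it with other starting values or another parameterisation.
2. If it still fails, use first-order ante-dependence, ANTE(1), ahead of the Toeplitz and AR(1) entries. It has 7 SDs and 6 adjacent-visit correlations, 13 parameters, the same number as heterogeneous Toeplitz. Keep heterogeneous compound symmetry only behind it.
3. Whenever the matrix is not unstructured, use the empirical (sandwich) variance with a compatible degrees-of-freedom method.
4. State that this list replaces the one in Protocol 10.3.3.1.

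Do not substitute a spatial-power structure on study week. It works if correlation decays purely with time, but gave a bias of +0.069 where correlation levelled off at 0.5.

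The cost is a few words and standard software options, with no new data. The changed degrees-of-freedom method is immaterial at this sample size. Two limits remain. The sandwich variance corrects the SE but not the bias. ANTE(1) reduces bias but may not remove it when dropout is earlier: with 25% dropout spread over Weeks 8–24 and correlation levelling off at 0.5 or 0.6 (assumed), arm-mean bias was −0.01 to −0.04, against +0.06 to +0.08 for heterogeneous Toeplitz.

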6.12.1.2. Sensitivity analyses for Missing Data

The primary objective will also be repeated utilizing HbA1c data in FAS at baseline and at the 40-week visit with the aid of an ANCOVA. The response variable will be the primary measure and model terms will include treatment, country, baseline concomitant oral antihyperglycemic medication use (metformin alone versus metformin plus SU) as fixed effects, and baseline HbA1c as a covariate. The ANCOVA analysis will be conducted with multiple imputation of missing primary measure (see Section 6.12.1.3 for details) and statistical inference over multiple imputation of missing data guided by Rubin (1987).

With the aid of the ANCOVA analysis 2-sided 97.5% CI for mean change in HbA1c from baseline to 40-week visit for (10 mg tirzepatide - insulin glargine) as well as for (15 mg tirzepatide - insulin glargine) will be derived. If the upper limit of the CI is $\leq 0.4\%$, then the respective dose of tirzepatide (10 mg and/or 15 mg) will be declared noninferior to insulin glargine relative to change in HbA1c from baseline.

6.12.1.3. Methods for Multiple Imputations

For ANCOVA sensitivity analyses, missing HbA1c data at the 40-week visit will be imputed based on “retrieved dropouts,” defined as patients who had their HbA1c value measured at the 40-week visit in the same treatment arm who prematurely discontinued study drug. If value of the imputed HbA1c change from baseline is $< -6.0\%$ or $> 6.0\%$, that value will be set to -6.0% or 6.0% , respectively, to avoid unrealistic imputed values.

6.12.1.4. Additional Analyses of the Primary Outcome

The primary MMRM analysis model will be repeated using the PP population as a sensitivity analysis. If the conclusion differs from that of EAS, the data and analyses will be further investigated.

Upon successfully establishing noninferiority of tirzepatide compared to insulin glargine, superiority of tirzepatide compared to insulin glargine relative to change in HbA1c from baseline will be evaluated (see Section 6.12.3).

6.12.2. Secondary Efficacy Analyses Subject to Type 1 Error Rate Control

6.12.2.1. Mean Change in HbA1c from Baseline at the 40 Week Visit

Noninferiority of 5 mg tirzepatide to insulin glargine will be conducted in a manner similar to Section 6.12.1.1. Assessment of Superiority of tirzepatide doses compared to insulin glargine will be conducted using the same statistical models as those used for evaluating the primary objective in Section 6.12.1.1. Decisions will be guided by the two-sided p-values for mean comparisons between tirzepatide doses and insulin glargine (see details in Section 6.12.3).

6.12.2.2. Mean Change in Body Weight from Baseline at the 40 week visit

The analysis for change in body weight from baseline (postbaseline – baseline) will be conducted in a manner similar to the primary analysis in Section 6.12.1.1. Baseline HbA1c concentration ($\leq 8.5\%$, $> 8.5\%$ [≤ 69 , > 69 mmol/mol]) will be used as a fixed factor in place of baseline HbA1c

as a covariate and baseline body weight will be used as an additional covariate in the statistical model. Least squares mean estimates of mean change in body weight from baseline will be plotted by nominal visit and by study treatment. For multiple imputation of missing values, if the imputed value of weight change from baseline is <-50 kg or >50 kg, then that value will be set to -50 kg or 50 kg, respectively, to avoid unrealistic imputed values.

6.12.2.3. Proportion of Patients Achieving HbA1c $<7\%$ at the 40 week Visit

The analysis will be conducted utilizing data using the EAS with missing values imputed from an MMRM model and then dichotomized. The MMRM model includes treatment, country, baseline concomitant oral antihyperglycemic medication use, visit, and treatment-by-visit interaction as fixed effects, and baseline HbA1c as a covariate. After dichotomizing continuous HbA1c, the data are analyzed using a logistic regression model with treatment, country, and baseline concomitant oral antihyperglycemic medication use as fixed effects, and baseline HbA1c as a covariate. In addition, longitudinal logistic regression with repeated measurements with country, baseline concomitant oral antihyperglycemic medication use, treatment, visit, and treatment-by-visit interaction as fixed effects, and baseline HbA1c as a covariate will also be provided using data in EAS. If the longitudinal logistic model does not converge due to a small number of events, logistic regression will be utilized to analyze the proportion of patients achieving HbA1c $<7\%$ at nominal visits.

Analyses also will be conducted utilizing HbA1c data in the FAS at baseline and at the 40-week visit with the aid of a logistic regression with multiple imputation of missing HbA1c data at the 40-week visit (see Section 6.12.1.3 for details). Model terms will include treatment, country, and baseline concomitant oral antihyperglycemic medication use as fixed effects, and baseline HbA1c as a covariate. Statistical inference over multiple imputations will be guided by Rubin (1987).

6.12.3. Type 1 Error Rate Control Strategy for Primary and Key Secondary Efficacy Analysis.

Type 1 error rate control strategy for evaluation of primary and key secondary objectives is illustrated in

Figure GPHO.6.1.

1. $H_{15,1}$, $H_{15,2}$, and $H_{15,3}$ are evaluated hierarchically each at a 2-sided 0.025 significance level conditioned on successfully achieving the preceding objective. In parallel,
2. $H_{10,1}$, $H_{10,2}$, and $H_{10,3}$ are evaluated hierarchically each at two-sided 0.025 significance level conditioned on successfully achieving the preceding objective.
3.
 - a) If all objectives in #1 and #2 above are successfully established, $H_{5,1}$, $H_{5,2}$, and $H_{5,3}$ are evaluated hierarchically, each at a 2-sided 0.05 significance level.

- b) If all objectives in only #1 or only #2 above are successfully established, $H_{5,1}$, $H_{5,2}$, and $H_{5,3}$ are evaluated hierarchically, each at a 2-sided 0.025 significance level.
4. If all objectives: $H_{5,1}$, $H_{5,2}$, and $H_{5,3}$ are successfully established and
- a) if all objectives in #1 and #2 above are successfully established, then $H_{10,4}$, $H_{15,4}$ and $H_{5,4}$, will be evaluated hierarchically each at two-sided 0.05 significance level conditioned on the successfully achieving the preceding objective.
 - b) If all objectives in only #1 or only #2 above are successfully established, then $H_{10,4}$, $H_{15,4}$, and $H_{5,4}$ will be evaluated hierarchically each at a 2-sided 0.025 significance level conditioned on successfully achieving the preceding objective.
5. If all objectives in #3 and #4 above are successfully established, and at least 1 objective from #1 or #2 above is not successfully established, recycle 100% of the unused alpha back to #1 or #2 above.

[figure not shown]

Figure GPHO.6.1. Type 1 Error control strategy for primary and key secondary efficacy endpoints.

